7.1.5.3 Post-Treatment Visits

End-of-Therapy is not a visit; assessments noted in [Section 6](#) must be completed upon the decision to discontinue a subject from study treatment.

Safety follow-up will be conducted via a telephone call at 30 days (\pm 5 days) and 90 days (\pm 5 days) for SAEs after the last dose of trial treatment to confirm the resolution of any ongoing events. Additional unscheduled visits may be considered as needed and at the discretion of the investigator.

All subjects will receive a 6-month course of oral trimethoprim/sulfamethoxazole or ampicillin for subjects with sulfa allergy to be initiated approximately 72 hours following the last dose of study treatment or at the time of study discontinuation. The dose of trimethoprim/ sulfamethoxazole consists of either 160 mg trimethoprim/800 mg sulfamethoxazole (DS) tablet administered three times a week or 80 mg trimethoprim/400 mg sulfamethoxazole administered daily. The dose of ampicillin consists of 500 mg four times daily for 6 months. Review the approved product labeling for trimethoprim/sulfamethoxazole and ampicillin, and monitor antibiotic tolerance as dosing adjustments may be necessary. During the 6-month post-treatment antibiotic period, AEs that occur, which are deemed by the Investigator to be related to *Lm* or antibiotic treatment along with the concomitant medications used to treat the AE(s), will be recorded on the eCRF.

Lm Surveillance Monitoring for the detection of *Lm* will be initiated at the completion of study treatment or at the time of study discontinuation, if earlier. The *Lm* Surveillance Monitoring period will consist of obtaining a blood sample to monitor CBC, CMP, including CRP and ESR, and blood cultures at regular intervals. This testing will be performed on all subjects who have received at least one dose of ADXS31-142. It will occur every 3 months (\pm 2 weeks) for 3 years beginning 3 months after the last dose of study treatment.

During the 3-year *Lm* Surveillance Monitoring period, if a persistent increase in CRP and/or ESR is observed with negative blood cultures for listeria during this time the subject should be evaluated and treated, as appropriate, for another possible cause. In the event that a definite cause has not been identified then subjects must continue to be

monitored closely, including additional testing and blood culture(s), for possible listeriosis. This testing may be performed at the investigative site or at another acceptable location following consultation with the Sponsor. During the *Lm* Surveillance Monitoring period all related labs with positive blood cultures for Listeremia and all concomitant medications used to treat the infection will be captured as AEs.

Every effort should be made to collect information regarding disease status until the start of new anti-cancer treatment, disease progression, or end of the study. Subjects who discontinue for reasons other than progressive disease will have post-treatment follow-up for disease status until disease progression, initiating an anti-cancer therapy, withdrawing consent or becoming lost to follow-up. After documented disease progression, each subject will be followed by telephone for safety. For subjects who discontinue treatment for reasons other than progression, [REDACTED] testing should continue every 4 weeks and imaging should continue every 12 weeks (\pm 1 week) until disease progression.

7.2 Assessing and Recording Adverse Events

An AE is defined as any untoward medical occurrence in a patient or clinical investigation subject administered a pharmaceutical product and which does not necessarily have to have a causal relationship with this treatment. An AE can therefore be any unfavorable and unintended sign (including an abnormal laboratory finding, for example), symptom, or disease temporally associated with the use of a medicinal product or protocol-specified procedure, whether or not considered related to the medicinal product or protocol-specified procedure. Any worsening (i.e., any clinically significant adverse change in frequency and/or intensity) of a preexisting condition that is temporally associated with the use of Advaxis' or Merck's product, is also an AE.

Changes resulting from normal growth and development that do not vary significantly in frequency or severity from expected levels are not to be considered AEs. Examples of this may include, but are not limited to, teething, typical crying in infants and children and onset of menses or menopause occurring at a physiologically appropriate time.

Advaxis' or Merck's product includes any pharmaceutical product, biological product, device, diagnostic agent or protocol-specified procedure, whether investigational (including placebo or active comparator medication) or marketed, manufactured by, licensed by, provided by or distributed by Advaxis or Merck for human use.

Adverse events may occur during the course of the use of an Advaxis or Merck product in clinical trials or within the 30-Day Follow-Up period, or prescribed in clinical practice, from overdose (whether accidental or intentional), from abuse and from withdrawal.

Adverse events may also occur in screened subjects during any pre-allocation baseline period as a result of a protocol-specified intervention, including washout or discontinuation of usual therapy, diet, placebo treatment or a procedure. All AEs will be recorded from the time the consent form is signed through the completion of the 30-Day Follow-Up period of the study or the initiation of a new anticancer therapy, whichever is

earlier. Adverse Events and SAEs experienced during this period will be reported and recorded in the eCRF. The reporting timeframe for AEs meeting any serious criteria is described in [Section 7.2.3.1](#).

7.2.1 Definition of an Overdose for This Protocol and Reporting of Overdose to the Sponsor

For purposes of this trial, an overdose will be defined as any dose exceeding the prescribed dose for ADXS31-142 or ≥ 1000 mg of pembrolizumab (MK-3475). No specific information is available on the treatment of overdose of ADXS31-142 or pembrolizumab (MK-3475). In the event of overdose, the subject should be observed closely for signs of toxicity. Appropriate supportive treatment should be provided if clinically indicated.

If an AE(s) is associated with (“results from”) an overdose, the AE(s) is reported as a SAE, even if no other seriousness criteria are met.

If an overdose is taken without any associated clinical symptoms or abnormal laboratory results, the overdose is reported as a non-serious ECI, using the terminology “accidental or intentional overdose without adverse effect.”

All reports of overdose with an AE must be reported within 24 hours to inVentiv Health Clinical Pharmacovigilance (Attn: iVH SAE Reporting; [contact] or email: [contact]).

7.2.2 Reporting of Pregnancy and Lactation to the Sponsor

Although pregnancy and lactation are not considered AEs, it is the responsibility of Investigators or their designees to report any pregnancy or lactation in a subject’s partner (spontaneously reported to them) that occurs during the trial or within 120 days of completing the trial, or 30 days following cessation of treatment if the subject initiates new anticancer therapy, whichever is earlier. All female partners of male subjects who become pregnant must be followed to the completion/termination of the pregnancy. Pregnancy outcomes of spontaneous abortion, missed abortion, benign hydatidiform mole, blighted ovum, fetal death, intrauterine death, miscarriage and stillbirth must be reported as SAEs (Important Medical Events). If the pregnancy continues to term, the outcome (health of infant) must also be reported.

Such events must be reported within 24 hours of awareness to inVentiv Health Clinical Pharmacovigilance (Attn: iHC SAE Reporting; [contact] or email: [contact])

7.2.3 *Immediate Reporting of Adverse Events to the Sponsor*

7.2.3.1 *Serious Adverse Events*

A SAE is any AE occurring at any dose or during any use of Advaxis' or Merck's product that:

- Results in death;
- Is life threatening;
- Results in persistent or significant disability/incapacity;
- Results in or prolongs an existing inpatient hospitalization;
- Is a congenital anomaly/birth defect;
- Is a new cancer (that is not a condition of the study);
- Is associated with an overdose;
- Is an important medical event

Refer to [Table 16](#) for additional details regarding each of the above criteria.

Progression of the cancer under study is not considered an AE unless it results in hospitalization or death.

Any SAE, or follow up to a SAE, including death due to any cause, that occurs to any subject from the time the consent is signed through the completion of the 90-Day Follow-Up period of the study, whether or not related to Advaxis' or Merck's product, must be reported within 24 hours of awareness to inVentiv Health Clinical Pharmacovigilance (Attn: iHC SAE Reporting; [contact] or email: [contact]).

Non-serious ECIs will be forwarded to inVentiv Health Clinical and will be handled in the same manner as SAEs. Concomitant medications administered to treat SAEs and ECIs should be recorded through the completion of the 30-Day Follow-Up period.

Additionally, any SAE, considered by an Investigator who is a qualified physician, to be related to the Advaxis' or Merck's product that is brought to the attention of the Investigator at any time outside of the time period specified in the previous paragraph also must be reported immediately to inVentiv Health Clinical Pharmacovigilance (Attn: iHC SAE Reporting; [contact] or email: [contact]).

SAE reports and any other relevant safety information are to be forwarded to: inVentiv Health Clinical Pharmacovigilance (Attn: iHC SAE Reporting; [contact] or email: [contact]).

Adverse Event reports meeting the requirements of a 7 Day Reports, 15 Day Reports, or the requirements for inclusion in the Annual Periodic Reports will be submitted as required to FDA, European Union (EU), Pharmaceutical and Medical Devices agency (PMDA) or other local regulators. Investigators will be provided a copy of the submission and will utilize this for submission to local IRB/ECs as required. The submission will cross reference the Sponsor's Investigational Compound Number (IND, CSA, etc.).

All subjects with SAEs must be followed up for outcome.

7.2.3.2 *Events of Clinical Interest*

Selected non-serious and SAEs are also known as ECIs and must be reported to the Sponsor. ECIs must be recorded as such on the Adverse Event CRFs/worksheets and reported within 24 hours to inVentiv Health Clinical Pharmacovigilance (Attn: iHC SAE Reporting; [contact] or email: [contact]).

ECIs for this trial include:

1. Overdose, as defined in [Section 7.2.1 - Definition of an Overdose for This Protocol and Reporting of Overdose to the Sponsor](#), which is not associated with clinical symptoms or abnormal laboratory results.
2. An elevated AST or ALT value that is $\geq 3X$ the upper limit of normal and an elevated total bilirubin value that is $\geq 2X$ the upper limit of normal and, at the same time, an alkaline phosphatase value that is $\leq 2X$ the upper limit of normal, as determined by way of protocol-specified laboratory testing or unscheduled laboratory testing.*
3. Cytokine release syndrome (CRS): Subjects presenting with all 6 symptoms of CRS that include nausea, headache, tachycardia, hypotension, rash, and shortness of breath.
4. Listeremia
5. Hypotension – \geq Grade 2
6. Any AE \geq Grade 3

*Note: These criteria are based upon available regulatory guidance documents. The purpose of the criteria is to specify a threshold of abnormal hepatic tests that may require an additional evaluation for an underlying etiology.

ECIs that occur in any subject from the date of first dose through 30 days following cessation of treatment, or the initiation of a new anticancer therapy, whichever is earlier, must be reported within 24 hours of awareness to inVentiv Health Clinical Pharmacovigilance (Attn: iHC SAE Reporting; [contact] or email: [contact]).

7.2.4 *Evaluating Adverse Events*

An Investigator who is a qualified physician will evaluate all AEs according to the CTCAE v 4.03. Any AE that changes CTCAE grade over the course of a given episode will have each change of grade recorded on the AE CRFs according to [Table 16](#). All AEs regardless of CTCAE grade must also be evaluated for seriousness. Symptoms associated with Cytokine Release Syndrome (CRS) which include *nausea, headache, tachycardia, hypotension, rash, and shortness of breath* MUST be reported as individual symptoms. If a subject manifest all five CRS symptoms, then CRS can be reported as a single event. Otherwise they must be reported individually as it is not a true CRS.

Table 16 Evaluating Adverse Events

V4.03 CTCAE Grading	Grade 1	Mild; asymptomatic or mild symptoms; clinical or diagnostic observations only; intervention not indicated.
	Grade 2	Moderate; minimal, local or noninvasive intervention indicated; limiting age-appropriate instrumental ADL.
	Grade 3	Severe or medically significant but not immediately life-threatening; hospitalization or prolongation of hospitalization indicated; disabling; limiting self-care ADL.
	Grade 4	Life threatening consequences; urgent intervention indicated.
	Grade 5	Death related to AE
Seriousness	A SAE is any AE occurring at any dose or during any use of Advaxis or Merck product that:	
	† Results in death; or	
	† Is life threatening; or places the subject, in the view of the investigator, at immediate risk of death from the event as it occurred (Note: This does not include an AE that, had it occurred in a more severe form, might have caused death.); or	
	† Results in a persistent or significant disability/incapacity (substantial disruption of one's ability to conduct normal life functions); or	
	† Results in or prolongs an existing inpatient hospitalization (hospitalization is defined as an inpatient admission, regardless of length of stay, even if the hospitalization is a precautionary measure for continued observation. (Note: Hospitalization [including hospitalization for an elective procedure] for a preexisting condition which has not worsened does not constitute a SAE.); or	
	† Is a congenital anomaly/birth defect (in offspring of subject taking the product regardless of time to diagnosis); or	
	Is a new cancer; (that is not a condition of the study) or	
	Is an overdose (whether accidental or intentional). Any AE associated with an overdose is considered a SAE. An overdose that is not associated with an AE is considered a non-serious event of clinical interest and must be reported within 24 hours.	
	Other important medical events that may not result in death, not be life threatening, or not require hospitalization may be considered a SAE when, based upon appropriate medical judgment, the event may jeopardize the subject and may require medical or surgical intervention to prevent one of the outcomes listed previously (designated above by a †).	
Duration	Record the start and stop dates of the AE. If less than 1 day, indicate the appropriate length of time and units	
Action taken	Did the AE cause the Advaxis or Merck product to be discontinued?	

Relationship to test drug	
Did the Advaxis or Merck product cause the AE? The determination of the likelihood that the Advaxis or Merck product caused the AE will be provided by an investigator who is a qualified physician. The investigator's signed/dated initials on the source document or worksheet that supports the causality noted on the AE form, ensures that a medically qualified assessment of causality was done. This initialed document must be retained for the required regulatory time frame. The criteria below are intended as reference guidelines to assist the investigator in assessing the likelihood of a relationship between the test drug and the AE based upon the available information.
 
The following components are to be used to assess the relationship between the Advaxis or Merck product and the AE; the greater the correlation with the components and their respective elements (in number and/or intensity), the more likely the Advaxis or Merck product caused the AE:
 

Exposure	Is there evidence that the subject was actually exposed to the Merck product such as: reliable history, acceptable compliance assessment (pill count, diary, etc.), expected pharmacologic effect, or measurement of drug/metabolite in bodily specimen?	

Time Course	Did the AE follow in a reasonable temporal sequence from administration of the Advaxis or Merck product? Is the time of onset of the AE compatible with a drug-induced effect (applies to trials with investigational medicinal product)?	

Likely Cause	Is the AE not reasonably explained by another etiology such as underlying disease, other drug(s)/vaccine(s), or other host or environmental factors	

	Exposure	Is there evidence that the subject was actually exposed to the Merck product such as: reliable history, acceptable compliance assessment (pill count, diary, etc.), expected pharmacologic effect, or measurement of drug/metabolite in bodily specimen?	Time Course	Did the AE follow in a reasonable temporal sequence from administration of the Advaxis or Merck product? Is the time of onset of the AE compatible with a drug-induced effect (applies to trials with investigational medicinal product)?	Likely Cause	Is the AE not reasonably explained by another etiology such as underlying disease, other drug(s)/vaccine(s), or other host or environmental factors
Exposure	Is there evidence that the subject was actually exposed to the Merck product such as: reliable history, acceptable compliance assessment (pill count, diary, etc.), expected pharmacologic effect, or measurement of drug/metabolite in bodily specimen?						
Time Course	Did the AE follow in a reasonable temporal sequence from administration of the Advaxis or Merck product? Is the time of onset of the AE compatible with a drug-induced effect (applies to trials with investigational medicinal product)?						
Likely Cause	Is the AE not reasonably explained by another etiology such as underlying disease, other drug(s)/vaccine(s), or other host or environmental factors						
Relationship to Advaxis or Merck product (continued)	
The following components are to be used to assess the relationship between the test drug and the AE: (continued)
 

Dechallenge	Was the Advaxis or Merck product discontinued or dose/exposure/frequency reduced? If yes, did the AE resolve or improve? If yes, this is a positive dechallenge. If no, this is a negative dechallenge. (Note: This criterion is not applicable if: (1) the AE resulted in death or permanent disability; (2) the AE resolved/improved despite continuation of the Advaxis or Merck product; or (3) the trial is a single-dose drug trial); or (4) Merck product(s) is/are only used one time.)	

Rechallenge	Was the subject re-exposed to the Advaxis or Merck product in this study? If yes, did the AE recur or worsen? If yes, this is a positive rechallenge. If no, this is a negative rechallenge. (Note: This criterion is not applicable if: (1) the initial AE resulted in death or permanent disability, or (2) the trial is a single-dose drug trial); or (3) Advaxis or Merck product(s) is/are used only one time).	

	Dechallenge	Was the Advaxis or Merck product discontinued or dose/exposure/frequency reduced? If yes, did the AE resolve or improve? If yes, this is a positive dechallenge. If no, this is a negative dechallenge. (Note: This criterion is not applicable if: (1) the AE resulted in death or permanent disability; (2) the AE resolved/improved despite continuation of the Advaxis or Merck product; or (3) the trial is a single-dose drug trial); or (4) Merck product(s) is/are only used one time.)	Rechallenge	Was the subject re-exposed to the Advaxis or Merck product in this study? If yes, did the AE recur or worsen? If yes, this is a positive rechallenge. If no, this is a negative rechallenge. (Note: This criterion is not applicable if: (1) the initial AE resulted in death or permanent disability, or (2) the trial is a single-dose drug trial); or (3) Advaxis or Merck product(s) is/are used only one time).		
Dechallenge	Was the Advaxis or Merck product discontinued or dose/exposure/frequency reduced? If yes, did the AE resolve or improve? If yes, this is a positive dechallenge. If no, this is a negative dechallenge. (Note: This criterion is not applicable if: (1) the AE resulted in death or permanent disability; (2) the AE resolved/improved despite continuation of the Advaxis or Merck product; or (3) the trial is a single-dose drug trial); or (4) Merck product(s) is/are only used one time.)						
Rechallenge	Was the subject re-exposed to the Advaxis or Merck product in this study? If yes, did the AE recur or worsen? If yes, this is a positive rechallenge. If no, this is a negative rechallenge. (Note: This criterion is not applicable if: (1) the initial AE resulted in death or permanent disability, or (2) the trial is a single-dose drug trial); or (3) Advaxis or Merck product(s) is/are used only one time).						

	NOTE: IF A RECHALLENGE IS PLANNED FOR AN ADVERSE EVENT WHICH WAS SERIOUS AND WHICH MAY HAVE BEEN CAUSED BY THE ADVAXIS OR MERCK PRODUCT, OR IF REEXPOSURE TO THE ADVAXIS OR MERCK PRODUCT POSES ADDITIONAL POTENTIAL SIGNIFICANT RISK TO THE SUBJECT, THEN THE RECHALLENGE MUST BE APPROVED IN ADVANCE BY THE U.S. CLINICAL MONITOR AS PER DOSE MODIFICATION GUIDELINES IN THE PROTOCOL.
Consistency with Trial Treatment Profile	Is the clinical/pathological presentation of the AE consistent with previous knowledge regarding the Advaxis or Merck product or drug class pharmacology or toxicology?
The assessment of relationship will be reported on the case report forms /worksheets by an investigator who is a qualified physician according to his/her best clinical judgment, including consideration of the above elements.	
Record one of the following	Use the following scale of criteria as guidance (not all criteria must be present to be indicative of an Advaxis or Merck product relationship).
Definite:	The event follows a reasonable temporal sequence from administration of the study drug, the event follows a known response pattern to the study drug and based on the known pharmacology of the study drug, the event is clearly related to the effect of the study drug
Probable:	The event follows a reasonable temporal sequence from administration of the study drug and the event follows a known response pattern to the study drug AND the event cannot have been reasonably explained by an intercurrent medical condition or the event cannot be the effect of a concomitant medication
Possible	The event follows a reasonable temporal sequence from administration of the study drug or the event follows a known response pattern to the study drug BUT the event could have been produced by an intercurrent medical condition which, based on the pathophysiology of the condition, and the pharmacology of the study drug, would be unlikely related to the use of the study drug or the event could be the effect of a concomitant medication
Unlikely	The event is clearly due to causes distinct from the use of the study drug, such as a documented pre-existing condition, the effect of a concomitant medication, a new condition which, based on the pathophysiology of the condition, and the pharmacology of the study drug, would be unlikely related to the use of the study drug
Unrelated	The event does not follow a temporal relationship to the study treatment administration (too early, late, or study treatment(s) not taken) or there is a reasonable causal relationship between another drug, concurrent disease, or circumstance and the AE

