5 METHODOLOGY

5.1 Entry Criteria

5.1.1 *Diagnosis/Condition for Entry into the Trial*

The study will be conducted in male subjects with histologically confirmed mCRPC who have progressed or become resistant to no more than 2 prior systemic treatment regimens with chemotherapy, targeted therapies, radiopharmaceuticals, or immunotherapy in the metastatic setting. Hormonal treatment will not be considered when determining the number of prior regimens in the metastatic setting. Subjects cannot have had more than 1 prior chemotherapeutic regimen in the metastatic setting. Subjects with evidence of progressive bone or other metastases are acceptable. Subjects may remain on castration therapy (luteinizing-hormone-releasing hormone [LHRH] agonist or antagonist) during the trial.

5.1.2 *Subject Inclusion Criteria*

In order to be eligible for participation in this trial, the subject must:

1. Be willing and able to provide written informed consent for the trial.
2. Be ≥ 18 years of age on day of signing informed consent.
3. Have progressive metastatic castration resistant prostate cancer, on androgen deprivation therapy, based on at least one of the following criteria:
 - a. PSA progression defined as 25% increase over baseline value with an increase in the absolute value of at least 2 ng/mL that is confirmed by another PSA level with a minimum of a 1-week interval with a minimum PSA of 2 ng/ml.
 - b. Progression of bi-dimensionally measurable soft tissue (nodal metastasis) assessed within 1 month prior to registration by a CT scan or MRI of the abdomen and pelvis (please refer to [Section 7.1.2.5.1](#) for definitions of measurable disease).

- c. Progression of bone disease (evaluable disease) (new bone lesion(s)) by bone scan. (Please refer to [Section 7.1.2.5.1](#) for definitions of evaluable disease).
4. Has discontinued antiandrogens (bicalutamide, nilutamide) >6 weeks and enzalutamide or abiraterone >4 weeks prior to Day 1 of trial treatment
5. Have a performance status of 0 or 1 on the ECOG Performance Scale.
6. Demonstrate adequate organ function as defined in [Table 3](#). All screening labs should be performed within 28 days of treatment initiation.

Table 3 Adequate Organ Function Laboratory Values

System	Laboratory Value
Hematologic	
Absolute neutrophil count (ANC) ^a	≥1000 /mcL
Platelets ^a	≥75,000 / mcL
Hemoglobin ^a	≥9 g/dL or ≥5.6 mmol/L
Lymphocytes	≥500 / mcL
Renal	

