5.2.1.2.2 ADXS31-142

The most likely anticipated AEs associated with ADXS31-142 are comprised primarily of individual flu-like symptoms (e.g., fatigue, lethargy and low grade fever) or cytokine release symptoms (e.g., constitutional symptoms such as fever, chills, rigors, headache, nausea, vomiting, tachycardia, shortness of breath, hypotension, and rash). These symptoms usually present within 2-4 hours after the completion of infusion and are often mild to moderate and transient in nature or respond quickly to symptomatic treatment. In rare instances, they may last up to 24 hours. No cumulative or delayed toxicity has been observed.

Less likely AE's include increase heart rate, low blood pressure, muscle aches, headaches, allergic reaction, changes in blood chemistry, changes in blood counts, and short term changes in liver function.

Rare but serious AEs include high fever, difficulty breathing and hypotension.

██████████ ADXS31-142 has a tropism for the liver. Transient asymptomatic elevations of ALT and alkaline phosphatase were observed after dosing with ADXS11-001 in the Phase 1 trial without prophylactic medication administration. For that reason, subjects with significant liver disease are excluded, and particular attention is to be paid to hepatic abnormalities.

The dose of ADXS31-142 will not be modified (e.g., reduced or increased) unless if it is determined that the toxicities are clearly attributed to ADXS31-142 or the combination, the treatment modification guidelines for drug-related AEs in [Table 9](#) shown below are to be followed.

Table 9 Treatment Delay/Discontinuation Guidelines for Drug-Related Adverse Events-ADXS31-142

Toxicity	Grade	Hold treatment	Timing for restarting treatment	Discontinue treatment
Hematologic	1-3	No	N/A	N/A
	4	Yes	Toxicity resolves to ≤Grade 1 or baseline	Toxicity does not resolve to ≤Grade 1 or baseline within 12 weeks
Non-hematologic, excluding cytokine release symptoms and DLTs	1	No	N/A	N/A
	2-3	Yes	Toxicity resolves to ≤Grade 1	Toxicity not resolved to ≤Grade 1 within 12 weeks of last infusion ^a
	4	N/A	Permanently discontinue treatment	Permanently discontinue treatment

^a With Investigator and Sponsor agreement, subjects with a non-heme AE (e.g., alopecia, neuropathy) still at grade 2 after 12 weeks, may continue treatment if only asymptomatic and controlled.

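### The liver-injury event of clinical interest cannot fire in a subject with ALP above 2x ULN, in a trial that accepts bone metastases and sets no ALP entry limit

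*Combined protocol and SAP*

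**What the plan says.** Section 7.2.3.2 (Events of Clinical Interest) lists six ECIs to be reported within 24 hours. Item 2 is the hepatic one. It needs three results together: AST or ALT at least 3x ULN, total bilirubin at least 2x ULN, and "at the same time, an alkaline phosphatase value that is" at most 2x ULN. It is triggered by laboratory values, scheduled or unscheduled. A note attributes the criteria to regulatory guidance and gives their purpose, which is to "specify a threshold of abnormal hepatic tests that may require an additional evaluation for an underlying etiology". Item 6 separately makes every AE of Grade 3 or higher an ECI, with no ALP condition.

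On the population, Section 5.1.1 states: "Subjects with evidence of progressive bone or other metastases are acceptable". New lesions on bone scan are one of three alternative ways to show progression at entry (Section 5.1.2, criterion 3). The hepatic rows of Table 3 limit bilirubin, AST and ALT, with AST/ALT allowed up to 5x ULN where there are liver metastases. There is no ALP row. ALP is measured (Table 15), but no test that separates bone from liver ALP is listed.

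On the liver, Section 5.2.1.2.2 says that ADXS31-142 has a tropism for that organ and asks for particular attention to hepatic abnormalities. It also reports, for a related product, "Transient asymptomatic elevations of ALT and alkaline phosphatase were observed after dosing with ADXS11-001".

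Section 4.2.3.2 names ECIs as part of the safety assessment. Section 8.2.3 plans summaries of AEs, DLTs and changes in serum chemistry. It lists no ECI table and no table of combined transaminase and bilirubin elevation.

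**The concern.** An ALP ceiling in a combined liver criterion makes sense if ALP reflects the liver, because a high value then suggests a cholestatic cause. In men with bone metastases, ALP can be high because of bone. The ceiling then removes a subject from the criterion for a reason unrelated to the liver, and item 2 makes no allowance for baseline ALP or for its source.

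This also works against the stated purpose. The criterion is meant to prompt a search for the cause, yet the ALP condition screens the case out before anyone looks, using a marker whose meaning is uncertain in this population.

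At stake is the completeness of one safety signal in a trial whose primary objective is safety. Item 2 is the only provision that looks at transaminases and bilirubin jointly. Where it is switched off, a non-serious combined elevation below Grade 3 gets no 24-hour report, and no listing marks the combination at any grade.

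**Working it through.** The plan gives no figure on this point, so there is none to reproduce. The check has three parts.

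**1. Logic of item 2.** Inputs are the three thresholds in Section 7.2.3.2. As written, item 2 fires if (AST or ALT ≥ 3x) AND (bilirubin ≥ 2x) AND (ALP ≤ 2x), all in multiples of ULN. Four illustrative profiles:

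| AST/ALT | Bilirubin | ALP | Item 2 as written | Without the ALP condition |
|---|---|---|---|---|
| 3x | 2x | 2x | fires | fires |
| 3x | 2x | 2.1x | does not fire | fires |
| 4x | 2.5x | 4x | does not fire | fires |
| 8x | 4x | 4x | does not fire | fires |

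The first two rows differ only in ALP. The last row shows that no degree of AST/ALT and bilirubin elevation overrides the ceiling. Nothing in the entry criteria keeps ALP at or below 2x ULN, so a subject can be in this state from the first dose.

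**2. What still catches such a case, whatever the ALP.**

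- Section 7.2: all AEs are recorded through the 30-day follow-up or new anticancer therapy.
- Section 7.2.3.2, item 6: an AE of Grade 3 or higher is reported within 24 hours.
- Section 7.2.3.1: SAEs are reported within 24 hours, including important medical events by judgment.
- Section 5.2.1.1.1: related non-hematologic toxicity of Grade 3 or higher within the window is assessed as a DLT.
- Section 7.1.3.1: laboratory results must meet Table 3 before each dose. In the 4x / 2.5x / 4x profile, AST/ALT exceeds the 2.5x limit (absent liver metastases) and bilirubin exceeds the 1.5x limit (unless direct bilirubin is normal).
- Tables 8 and 9 and the hepatic care guidance in Section 5.6.1.6 act from Grade 2 and carry no ALP condition.

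Subtracting these leaves two losses: 24-hour reporting of combined elevations that are non-serious and below Grade 3, and the joint flag at any grade. Item 6 reports a Grade 3 or higher event but does not identify it as a transaminase-bilirubin combination. How wide the band below Grade 3 is depends on CTCAE v4.03 cut-offs, which the documents do not print.

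**3. How many subjects could be exposed.** The share f of subjects with ALP above 2x ULN is not in the documents. Take f from 5% to 40% as an assumption. Expected number = N × f. Chance of at least one = 1 − (1 − f)^N, with subjects treated as independent.

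- N = 30 (combination at the RP2D, Section 5.2.1.1.3): 30 × 0.05 = 1.5 and 30 × 0.40 = 12. At f = 5%, 1 − 0.95^30 = 0.785.
- N = 51 (whole trial, Section 1): 51 × 0.05 = 2.55 and 51 × 0.40 = 20.4. At f = 5%, 1 − 0.95^51 = 0.927.

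These are subjects in whom item 2 cannot fire. They are not predicted events, because the documents give no rate for combined elevation. Section 5.2.1.1.2 says Part A is complete, so the N = 30 figures are the ones relevant to a change.

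**The case against.** The strongest reply is that little depends on item 2. It is an expedited-reporting threshold, not an analysis endpoint. Section 8.2.3 has no ECI table, no inferential analysis is planned, and the data needed for a combined table are collected anyway. The safeguards listed in the working cover recording, dosing decisions and the more severe events. All of this stands, and it confines the point to reporting and tabulation.

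A reader might infer that liver signals are discarded in subjects with high ALP. The documents do not support that, because those same safeguards operate whatever the ALP.

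A reader might also infer from Section 5.2.1.2.2 that dosing is known to raise ALP, so that a combined rise with high ALP is the pattern to expect. The text does not go that far. It concerns ADXS11-001 in a Phase 1 trial without prophylactic medication, whereas this trial requires premedication. It calls the rises transient and asymptomatic, gives no size, does not say that ALT and ALP rose together in the same subjects, and does not mention bilirubin. The point therefore rests on bone disease and the absence of an ALP entry limit.

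Finally, the ALP condition is deliberate and is attributed to regulatory guidance. That is a fair reason for keeping the present criterion visible in the output. It does not answer the difficulty, because the note says nothing about a population in which ALP may be raised by bone.

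**Conclusion.** The point holds in a narrow form. By its own wording, ECI item 2 cannot fire in a subject whose ALP is above 2x ULN, including one whose ALP was already raised at baseline by bone disease, and the entry criteria allow such subjects. That follows from the text and needs no assumption about frequency.

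The consequence is limited to the two losses identified: expedited reporting of non-serious combined elevations below Grade 3, and the joint flag at any grade. Under the assumed 5 to 40% share, about 1.5 to 12 of 30 combination subjects would be exposed to the gap. The share could lie outside that range, and the number of events actually missed cannot be estimated and could be close to zero. It is a modest defect, worth correcting because the trial's primary purpose is safety and the correction is cheap.

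**What to change.** Change reporting and tabulation only, for Part B going forward.

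1. In Section 7.2.3.2, report AST/ALT at least 3x ULN with total bilirubin at least 2x ULN as item 2 regardless of ALP when baseline ALP is above 2x ULN, or, more simply, in all subjects. The baseline version still misses a subject whose ALP passes 2x ULN after entry; the all-subjects version does not.
2. Record current and baseline ALP with each such report, so that a cholestatic or bone explanation can be judged afterwards.
3. In Section 8.2.3, add one table of combined AST/ALT and bilirubin elevation, with and without the ALP condition. The count under the present criterion then remains available.

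The cost is one sentence, one table from laboratory data already collected, and a few extra 24-hour reports with a cholestatic or tumor cause. These would arise notably in subjects with liver metastases: they may enter with AST/ALT up to 5x ULN, so some already meet the transaminase condition, and without the ALP condition item 2 would then turn on bilirubin alone. The recorded baseline values allow such reports to be recognised.
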